8.6 Measures of treatment compliance

All subjects are inpatients with all administered medications being recorded. Missed doses and total amount of doses administered will be recorded for the study. The study monitor will review this data throughout the course of the study.

8.7 Standard of care treatment with tobramycin

Subjects will receive intravenous tobramycin in accordance with standard procedures established through the Department of Pharmacy and Department of Nursing at National Jewish Health | Saint Joseph Hospital. It is administered through a peripheral IV, peripherally inserted central catheter (PICC line), or indwelling port.

8.7.1 Administration instructions: Intravenous tobramycin will be administered as per standard care³⁵ on a weight-based dosing regimen. The amount to be given to each patient who is prescribed tobramycin is based on standard treatment recommendations of 8-10 mg/kg/day as a one time dose daily. The precise dose is determined by the CF clinical pharmacist and treating physician, based on previous experiences with dosing of the drug and previous doses which achieved levels within treatment guidelines for that individual. Precise administration instructions are as follows:

Tobramycin (X-gen Pharmaceuticals) is reconstituted in a 1.2 gram vial with 30 cc of sterile water for injection with resultant solution of 40 mg/ml. The appropriate dose is drawn up in a syringe and injected into 100 ml normal saline piggy back. The medication is infused over 30 min. Tobramycin peaks and troughs are drawn with the second dose of tobramycin. Dose adjustment will occur to achieve non-detectable troughs, and peaks 20-30 mg/dL². Tobramycin concentrations are assessed once weekly during each week of APE treatment.

8.8 Standard of care treatment with colistin

Subjects will receive intravenous colistin in accordance with standard procedures established through the Department of Pharmacy and Department of Nursing at National Jewish Health | Saint Joseph Hospital. It is administered through a peripheral IV, peripherally inserted central catheter (PICC line), or indwelling port.

8.8.1 Administration instructions: Intravenous colistin will be administered as per standard care^{1,24} on a weight-based dosing regimen. The amount to be given to each patient who is prescribed colistin is based on standard treatment recommendations of 3-5 mg/kg/day, divided into 3 doses. The precise dose is determined by the CF clinical pharmacist and treating physician, based on maximal dosing within the reference range tolerated by the individual and without evidence of toxicities. Precise administration instructions are as follows:

Colistin powder in a 150 mg vial is reconstituted with 2 ml of sterile water for injection with resultant solution concentration of 75mg/ml. The desired dose is drawn up in an appropriate syringe and then injected into 50 cc normal saline piggy back. The medication is infuse over 30 minutes. There are no pharmacokinetic measurements to guide standard dosing; however, plasma, sputum, and urine will be collected and analyzed from the subjects in this treatment arm on the same schedule as the modified colistin arm to serve as study controls. Treatment is guided by evidence of toxicity (either

nephrotoxicity or neurotoxicity), based on clinical exam and on serum and urine studies.

8.9 Pharmacokinetic driven treatment with colistin.

Subjects will receive intravenous colistin in accordance with standard procedures established through the Department of Pharmacy and Department of Nursing at National Jewish Health | Saint Joseph Hospital. It is administered through a peripheral IV, peripherally inserted central catheter (PICC line), or indwelling port. The main difference between this study group and the standard colistin group will be the measurements of drug levels and adjustments to dosing based on results.

8.9.1 Administration instructions: Intravenous colistin will be administered as per standard care^{1,24} on a weight-based dosing regimen; however, instead of dosing three times daily, dosing will be on a twice daily schedule. The total amount to be given to each patient who is prescribed colistin will still be standard treatment recommendations of 3-5 mg/kg/day, but divided into 2 doses. The precise dose is determined by the CF clinical pharmacist and treating physician, based on previous experiences with dosing of the drug and previous doses which achieved levels within treatment guidelines for that individual, if that information is available. Precise administration instructions are as follows:

Colistin powder in a 150 mg vial is reconstituted with 2 ml of sterile water for injection with resultant solution concentration of 75mg/ml. The desired dose is drawn up in an appropriate syringe and then injected into a 50 cc normal saline piggy back bag. It is infused over 30 minutes. Steady state plasma concentrations on visit 2 of therapy (on 2nd-3rd dose once at goal dosing) will be measured; specifically, colistin peak (30-60 minutes after infusion), midpoint (4-6 hours after dosing) and/or trough (30-0 minutes prior to next infusion). A steady state sputum sample will be procured at visit 2 to assess epithelial lining concentrations, unless subjects are on inhaled colistin as this will create inaccuracies in colistin sputum concentration measurements. Levels of colistin A and B and pro-drug from plasma, sputum, and urine will be quantified in the University of Colorado School of Pharmacy Medicinal Chemistry Core, with a 36 hour turnaround time to allow for measurement and interpretation. [name] at the School of Pharmacy will determine the optimal dose and intervals for APE subjects based on PK modeling with feedback from the PI, treating physician, and the National Jewish Health | Saint Joseph Hospital inpatient pharmacists. Colistin concentrations in plasma, sputum, and urine will be re-assessed at visit 3, after PK adjusted optimal dosing of colistin has reached a steady state.

9. Study Procedures and guidelines

A Schedule of Events representing the required testing procedures to be performed for the duration of the study is diagrammed below.

TABLE 3: Timing of study assessments

	Visit 1	Visit 2	Visit 3	Visit 4
Informed Consent and Eligibility Review	X			
Demographics	X			
Medical History and Concomitant Medications	X			X
Physical Exam and Vital Signs	X	X	X	X
Questionnaires	X			X
Spirometry	X			X
Blood labs	→	→	→	→
Urine labs	→	→	→	→
Sputum microbiology	X			X
Blood collection for pharmacokinetic analysis (PK)		X	X	
Sputum collection for pharmacokinetic analysis (PK)		X	X	
Urine collection for pharmacokinetic analysis (PK)		X	X	
Urine collection for Nephrocheck	X	X	X	X

Prior to conducting any study-related activities, written informed consent and the Health Insurance Portability and Accountability Act (HIPAA) authorization must be signed and dated by the subject or subject's legal representative.

9.1 Clinical assessments

9.1.1 Concomitant Medications

All concomitant medication and concurrent therapies will be documented as noted in the Schedule of Events. Dose, route, unit, frequency of administration, and dates of medication will be captured. The total number of IV doses of tobramycin and colistin for each study arm will be recorded.

9.1.2 Demographics

Demographic information (date of birth, sex, race) will be recorded at Visit 1.

9.1.3 Medical History

Relevant medical history, including history of current disease, other pertinent respiratory history, and information regarding underlying disease will be recorded at Visit 1.

9.1.4 Physical examination

A complete physical examination will be performed by either the investigator or a CF physician as noted in the Schedule of Events. An exacerbation score will be calculated for each subject, in order to quantify severity of exacerbation, using the validated Rosenfeld score. Any new clinically significant abnormal physical exam findings must be documented as adverse events (AEs) and will be followed by the physician rounding on the service at each scheduled daily visit.

9.1.5 Vital signs

Resting measurements of body temperature, blood pressure, pulse, and respirations will be performed and recorded as noted in the Schedule of Events.

9.1.6 Spirometry

Spirometry will be performed as noted in the Schedule of Events and in accordance with the current American Thoracic Society recommendations for the performance and interpretation of tests.

Subjects who are in the hospital routinely receive nebulized bronchodilators four times daily. Every effort will be made to check study spirometry within the same window, late morning, after the initial bronchodilator treatment, for study subjects in all arms.

9.1.7 Subject Questionnaire: Cystic Fibrosis Questionnaire-Revised (CFQ-R)

The CFQ-R is a patient reported quality of life (QoL) instrument, regarding symptoms and mood over the preceding 2 weeks. The CFQ-R takes approximately 15 minutes to complete. This questionnaire will be completed by the subject at the beginning and end of study participation.

9.1.8 Pulmonary exacerbation evaluation

The number of subsequent diagnoses of acute pulmonary exacerbations and the amount of time between exacerbations in the year following study enrollment will be documented.

9.1.9 Adverse Events

Information regarding occurrence of adverse events will be captured throughout the study. A case report form (CRF) will be completed by the rounding physician, which will include signs and symptoms related to specific toxicities due to tobramycin or colistin. Severity, seriousness, outcome, treatment, and relation to study participation will be recorded.

9.2 Clinical Laboratory Measurements

9.2.1 Blood chemistry profile

Blood will be obtained as part of standard of care and sent to the clinical chemistry lab for determination of serum sodium, potassium, chloride, bicarbonate, random glucose, BUN, creatinine, aspartate aminotransferase (AST), alanine aminotransferase (ALT), alkaline phosphatase, total bilirubin, direct bilirubin, and albumin. All of the results will be recorded as part of the study.

9.2.2 Pregnancy test

Urine or blood, if necessary, will be collected from females who are of childbearing age for a pregnancy test as part of standard of care and tested in clinic according to site standard procedures. The results will be recorded as part of the study.

9.2.3 Tobramycin Pharmacokinetic Measurements

Blood will be obtained as part of standard of care and sent to the clinical chemistry lab for determination of peak and trough tobramycin concentrations on the second dose, followed by a second peak and trough during the second week of IV tobramycin therapy. Drug concentrations will be determined at National Jewish Health | Saint Joseph Hospital. The results will be recorded as part of the study.

9.2.4 Qualitative bacteriology

Sputum will be collected for culture as part of standard of care. All sputum specimens will be collected in a sterile specimen cup, labeled, and sent to the National Jewish Health | Saint Joseph Hospital's microbiology lab on the day of collection. Culture and sensitivities for typical CF pathogens is performed. The results will be recorded as part of the study.

9.2.5 Urine studies

Urine will be obtained as part of standard of care and sent to the clinical chemistry lab for determination of urine protein and urine protein:creatinine ratio. All of the results will be recorded as part of the study.

9.3 Research Laboratory Measurements

9.3.1 Colistin Pharmacokinetic Measurements (blood, sputum, and urine)

Blood, sputum, and urine will be obtained as noted in the Schedule of Events. Measurements of pharmacologically active colistin levels will be performed by LC-MS/MS in the University of Colorado School of Pharmacy Medicinal Chemistry Core. Prior to mass spectrometry measurement of the sputum specimen, it will be processed as per standard Cystic Fibrosis Therapeutic Development Network protocols.

9.3.2 Nephrotoxic Acute Kidney Injury assay (urine)

Urine will be obtained as noted in the Schedule of Events and will undergo cryopreservation. In patients who develop acute kidney injury (elevation of serum creatinine ≥ 0.3 mg/dL) urine will be thawed and evaluated for neutrophil gelatinase-associated lipocalin (NGAL) and tissue-inhibitor of metalloproteinase 2 (TIMP-2) and insulin-like growth factor binding protein 7 (IGFBP-7). NGAL will be evaluated by enzyme-linked immunosorbent assay (ELISA). TIMP-2 and IGFBP-7 will be measured by the Nephrocheck® assay. Nephrocheck® is a newly FDA approved assay for detection of nephrotoxic acute kidney injury and will be tested for its sensitivity and specificity for detection of acute kidney injury in CF within the study. Both assays will be run by the University of Colorado Renal Division.

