15.3 Safety analysis: The safety profile of each colistin arm and the tobramycin arm will be assessed in terms of the following: incidence of acute kidney injury (AKI), incidence of treatment related clinical events (ototoxicity, vestibular toxicity, and neurotoxicity). Adverse event rates will be compared between treatment groups using logistic regression, adjusting for age, medications such as vancomycin, baseline FEV₁, admits in the previous year, exposure to nephrotoxic antibiotics in the previous 5 years, and diagnosis of CF related diabetes (CFRD) as covariates. Repeated measures within subjects will be accounted for by including a random intercept for subjects. Summary statistics and changes from admission will be presented for serum creatinine and urine:protein ratios. The urine protein:creatinine ratio will be assessed as a

biomarker of drug toxicity. There are no published criteria for cessation of therapy or accurate prediction of AKI as a result of the urine protein values. Thus, this data will be analyzed as a predictor for AKI. We will analyze Nephrocheck® assay results in a case control design. Subjects who develop AKI within each of the study arms will have urine thawed and analyzed by Nephrocheck® and those results will be compared to age, gender, and FEV₁ matched control urines obtained from subjects within the study who did not develop AKI. An adjusted odds ratio will be derived from a model fitted with unconditional logistic regression and adjusted for confounding variables. Estimates of odds ratios and 99% confidence intervals will be presented.

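### Section 9.3.2 promises sensitivity and specificity for Nephrocheck, but section 15.3 plans only an odds ratio against matched controls, and NGAL is run in AKI cases with no comparator and no analysis

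*Combined protocol and SAP*

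**What the plan says.** Section 9.3.2 says of urine storage: "Urine will be obtained as noted in the Schedule of Events and will undergo cryopreservation". Table 3 and section 10 schedule a Nephrocheck urine collection at each of Visits 1 to 4, with no restriction by arm or AKI status. On testing, section 9.3.2 says: "In patients who develop acute kidney injury (elevation of serum creatinine ≥ 0.3 mg/dL) urine will be thawed and evaluated". The markers listed are NGAL (by ELISA) and TIMP-2 and IGFBP-7 (by Nephrocheck). It then says that Nephrocheck "will be tested for its sensitivity and specificity for detection of acute kidney injury in CF within the study". It mentions no thawing of urine from subjects without AKI.

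Section 15.3, repeated in the synopsis, says: "We will analyze Nephrocheck® assay results in a case control design". The comparison group is age-, gender- and FEV1-"matched control urines obtained from subjects within the study who did not develop AKI". The output is described in two sentences: "An adjusted odds ratio will be derived from a model fitted with unconditional logistic regression and adjusted for confounding variables" and "Estimates of odds ratios and 99% confidence intervals will be presented".

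Secondary objective 6 (section 3.2) seeks markers that signal nephrotoxic AKI before creatinine rises. It names the urine protein:creatinine ratio and Nephrocheck. NGAL does not appear in the objectives, the endpoints or section 15. The documents give no assay cut-off, no rule for which visit's sample is tested, no ratio of controls to cases, and no sensitivity, specificity or ROC analysis.

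**The concern.** The laboratory section sets a diagnostic-accuracy aim, and the statistical section plans a measure of association. If the plan is followed as written, the report will contain an odds ratio and no accuracy figure.

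Three further gaps follow.

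- **Whose urine is thawed.** A laboratory working from section 9.3.2 alone would test no controls. One working from section 15.3 would test controls with Nephrocheck but not NGAL.
- **What specificity would refer to.** Controls chosen to resemble the cases on age, gender and FEV1 give a false-positive rate for case-like subjects. That need not be the rate among all non-AKI subjects in the trial.
- **When the sample was taken.** Detection before the creatinine rise is the stated objective, but with up to four stored samples per subject, nothing says which one counts.

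If cut-off and sample are chosen after the results are seen, any accuracy figure reported will tend to be too favourable.

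**Working it through.** The documents state no sample size, power or precision for the assay work, so there is no figure of the plan's own to reproduce. The check has four steps.

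**1. Does an odds ratio fix accuracy?** For a dichotomised assay,

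OR = [sens / (1 − sens)] × [spec / (1 − spec)].

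- sens 50%, spec 90%: (0.5/0.5) × (0.9/0.1) = 1 × 9 = 9
- sens 75%, spec 75%: (0.75/0.25) × (0.75/0.25) = 3 × 3 = 9
- sens 90%, spec 50%: (0.9/0.1) × (0.5/0.5) = 9 × 1 = 9

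One odds ratio covers three very different tests, so the planned output does not deliver the promised quantities.

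**2. How many cases?** Inputs: 30 subjects per group (section 15.4); AKI incidence of 19% on tobramycin and 12% on colistin in the retrospective cohort (section 1.1). The PK-adjusted arm has no stated rate, so I assume 12% and show a range.

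- PK arm 12%: 30 × (0.19 + 0.12 + 0.12) = 12.9 cases, 90 − 12.9 = 77.1 non-cases
- PK arm 6%: 30 × (0.19 + 0.12 + 0.06) = 11.1 cases
- PK arm 19%: 30 × (0.19 + 0.12 + 0.19) = 15.0 cases

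**3. What precision would accuracy have?** Exact (Clopper-Pearson) 95% intervals with 13 cases. The control ratio is an assumption, because none is stated.

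| Quantity | Result | 95% CI |
|---|---|---|
| Sensitivity, 13 cases | 10/13 (77%) | 46% to 95% |
| Specificity, 1:1 controls | 12/13 (92%) | 64% to 99.8% |
| Specificity, 2:1 controls | 24/26 (92%) | 75% to 99% |
| Specificity, 3:1 controls | 36/39 (92%) | 79% to 98% |
| Specificity, all non-AKI | 71/77 (92%) | 84% to 97% |
| Specificity, all non-AKI | 69/77 (90%) | 81% to 95% |

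**4. NGAL.** Under section 9.3.2 it is run only in subjects who develop AKI, and section 15.3 does not extend it to controls. The number of non-AKI subjects with an NGAL result is therefore 0, and neither a specificity nor an odds ratio can be formed.

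**The case against.** The strongest reply is that the promise can be kept with the data the plan already collects. The accuracy sentence concerns Nephrocheck only, and section 15.3 supplies Nephrocheck results in cases and in non-AKI controls. Sensitivity and specificity are each conditional on AKI status, so a case-control sample yields both. This stands. A reader might infer that accuracy cannot be estimated, and the documents do not support that.

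Several other strong readings also fail.

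- **NGAL.** A reader might infer that the NGAL results support no inference. The documents never promise NGAL accuracy, and with urine stored at four visits a within-case change from baseline is possible, although no passage says which samples are thawed. What remains is the missing comparator and the missing analysis.
- **The 99% interval.** Section 15.2 sets a 0.05 level subject to exceptions noted elsewhere, and section 15.3 notes one. This is a choice, not an inconsistency.
- **Unconditional regression.** The documents do not say that matching is individual. An unconditional model containing the matching factors is acceptable for frequency or loose matching. The plan adjusts for confounders without naming them, so it is not established that the matching is ignored.

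Two points limit the size of the concern. The 1:1 ratio is the least favourable case; at 3:1 most of the precision gap closes. Specificity in matched controls differs from that in all non-AKI subjects only if false positives vary with age, gender or FEV1, and the documents give no evidence either way.

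**Conclusion.** The concern holds as a gap between a stated aim and the planned analysis. Nephrocheck sensitivity and specificity are promised but not planned, and the odds ratio that is planned cannot stand in for them. Sections 9.3.2 and 15.3 disagree on whose urine is thawed. NGAL has neither a comparator nor an analysis.

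Sensitivity and specificity could still be computed afterwards from the section 15.3 sample. They would lack a pre-stated cut-off and sample time, specificity would describe case-like controls, and with 13 controls its interval would run from about 64% to nearly 100%. Testing all non-AKI subjects narrows this to about 81% to 95%. Sensitivity stays imprecise under any choice of controls, because it rests on roughly 11 to 15 cases.

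These sizes assume that the retrospective AKI rates carry over, that the PK-adjusted arm lies between 6% and 19%, and, for the widest interval, 1:1 matching. The conclusion that the aim has no matching analysis needs none of these assumptions. Nothing here bears on the comparison of AKI rates or FEV1 between arms. The change should be made because it is cheap and lets the trial answer a question it has set itself.

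**What to change.** - **Align the sections.** State in 9.3.2, 15.3 and the synopsis, in the same terms, whose urine is thawed and for which assays.
- **Plan the promised analysis.** Make sensitivity and specificity the Nephrocheck analysis, at a cut-off and sample time fixed before any assay is run, with exact 95% CIs. The sample in cases should precede the creatinine rise, as secondary objective 6 requires, and the rule for choosing the visit in controls should be stated too.
- **Choose controls for specificity.** Test the stored urine of all non-AKI subjects, or of a random sample of stated size, so that specificity refers to the trial's non-AKI population.
- **Settle NGAL.** Run it on the same case and control urines with the same analysis, or drop it.
- **Keep the odds ratio as secondary.** If matching is retained, state the ratio and put the matching factors in the model.

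The cost is assays and wording, with no new sampling. At one sample per subject, testing everyone means about 90 Nephrocheck assays instead of about 26 at 1:1 (64 more), and about 90 NGAL assays instead of about 13 (77 more). A random sample of controls costs less and gives correspondingly wider intervals.

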10 EVALUATIONS BY VISIT

10.1 Visit 1

1. Review the study with the subject (or subject's legal representative) and obtain written informed consent and HIPAA authorization.
2. Administer QoL questionnaire
3. Review respiratory culture results in the previous 12 months
4. Assign the subject a unique identification number.
5. Record demographics data.
6. Record medical history, including exacerbation criteria based on Rosenfeld score, baseline serum creatinine, and number of exacerbations in the preceding year.
7. Record concomitant medications.
8. Perform a complete physical examination.
9. Obtain and record vital signs.
10. Record oximetry.
11. Record results from blood and urine clinical laboratory tests (chemistry, hematology).

12. Record results from urine or blood pregnancy test (if female of child-bearing potential).
13. Record results from spirometry.
14. Record results from sputum culture microbiology.
15. Collect urine for Nephrocheck®

10.2 Visit 2

1. Administer QoL questionnaire
2. Record serum creatinine from daily clinical laboratory draws.
3. Collect urine for Nephrocheck®
4. Record urine protein from three times weekly clinical laboratory check.
5. Record tobramycin peak and trough from week 1 clinical laboratory draw
OR
Collect blood, sputum, and urine for colistin pk measurement.

10.3 Visit 3

1. Administer QoL questionnaire
2. Record serum creatinine from daily clinical laboratory draws.
3. Collect urine for Nephrocheck®
4. Record urine protein from three times weekly clinical laboratory check.
5. Record tobramycin peak and trough from week 2 clinical laboratory draw
OR
Collect blood, sputum, and urine for colistin pk measurement.

10.4 Visit 4

1. Administer QoL questionnaire.
2. Record concomitant medications.
3. Record spirometry.
4. Record serum creatinine from daily clinical laboratory draws.
5. Record results from sputum culture microbiology.
6. Record total number of IV antibiotics doses over the preceding 14 days.
7. Collect urine sample for Nephrocheck®.
8. Complete Case Report Form (for toxicities).

